1.5 Pharmacokinetics and Product Metabolism in Animals

Absorption

Following intravenous (IV) administration, TBAJ-876 exhibited low clearance and a large volume of distribution (\geq 9.45 L/kg). The plasma disposition of TBAJ-876 in nonclinical species was multiexponential and due to differences in PK sampling schedule, estimates of terminal half-life ($t_{1/2}$) of TBAJ-876 varied widely, ranging from 5 to 12 hr (sampling out to 24 hr postdose) to 26 to 77 hr (sampling out to 96 hr postdose).

TBAJ-876 free base had good oral bioavailability ranging from 36% to 44% in rodents, 28% to 80% in dogs, and 19% to 24% in monkeys, despite low permeability in the Caco-2 cell monolayer. Based on the efflux ratio of 0.2 in Caco-2 cells, TBAJ-876 was not a substrate of efflux pumps.

^{**}Predicted clinical exposures of the highest proposed single clinical dose of 400 mg: C_{max} (Day 1) for TBAJ-876 and TBAJ-876-M3 of 0.688 and 0.104 μ g/mL, respectively; and AUC_{0-24h} = 10.4 and 2.08 μ g.hr/mL, respectively.

When TBAJ-876 was orally administered as tartrate salt to nonclinical species in the fasted state, C_{max} increased 40% to 70% and AUC_{0-t} increased 39% to 59% in rats and dogs, whereas in monkeys C_{max} and AUC_{0-t} decreased 43% and 49%, respectively.

The in vivo exposure to two active metabolites, TBAJ-876-M2 and TBAJ-876-M3, was quantified in the PK and toxicokinetic (TK) studies. At the NOAELs in the 13-week toxicology studies in the rat and dog, the steady state AUC of TBAJ-876-M3 was 0.6x and 1.8x of parent AUC, respectively, while TBAJ-876-M2 was present at lower concentrations with AUC representing 0.2 x of parent AUC in both species. There was no marked sex-related difference in the systemic exposure to TBAJ-876, TBAJ-876-M3, or TBAJ-876-M2 in rats and dogs.

In mice following the last dose of 4-week dosing at 3.125 mg/kg, steady state plasma exposure to TBAJ-876 and metabolites was approximately 0.4x of that of BDQ and metabolite at 25 mg/kg. After 6 weeks dosing in a mouse model of chronic TB, 3.125 mg/kg TBAJ-876 showed superior efficacy to 25 mg/kg BDQ indicative of TBAJ-876 being more potent than BDQ (Table 5). TBAJ-876-M3, TBAJ-876-M2, and BDQ-M2 AUC₀₋₂₄ was 5x of parent AUC_{0-24h}.

Table 5 Plasma Exposure to TBAJ-876 and Metabolites vs. BDQ and BDQ-M2 Following 4-week Repeated Oral Administration to Mice

Dose Analyte	C _{max} (μg/mL)	AUC _{0-24h} (hr*μg/mL)
3.125 mg/kg/day TBAJ-876		
TBAJ-876	0.47	4.1
TBAJ-876-M2	0.93	20.2

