3 STUDY DESIGN SUMMARY

This study is a three-part, partially blinded, placebo controlled, combined single ascending dose (SAD) with food-effect, multiple ascending dose (MAD) study, and a single dose relative bioavailability (BA) study conducted in one study center in the United States.

Safety will be assessed throughout the study for all subjects. Safety assessments will include physical examinations, vital signs, serial ECGs, cardiac monitoring, adverse events (AEs), and clinical laboratory tests (including hematology, serum chemistry, coagulation, and urinalysis).

Part 1:

Part 1 is a SAD design with 6 planned dose levels. Additional cohorts may be enrolled if deemed appropriate by the Sponsor to repeat a dose level or study another dose level. Interim PK analyses and safety assessments will be performed for the dose escalation decisions and to select the dose level at which to assess the food-effect. The food-effect cohort is planned with two parallel groups, one fasting and the other fed.

Current duration and scheduling of safety and PK sampling assumes that the terminal half-life ($T_{1/2}$) will be approximately 7 days. The number and timing of PK sampling and safety assessments may be further revised based on evolving PK and safety information.

Subjects will be housed in the clinic from at least 24 hours prior (from Day -1), until 7 days after dosing (Day 8).

Subjects from Dose Level 1 will return to the clinic to have subsequent follow up safety (collection of AEs) and PK assessments on Days 10, 14, 17, 21, and 28.

Food-Effect: Based on exposure levels from the first 4 completed cohorts, the 100 mg dose was chosen for the food-effect cohort. In this food-effect cohort, there will be two parallel groups, one fasting and the other fed. The fed group will enroll at least 10 subjects and the fasted group will include data from 6 subjects who completed Cohort 4 and at least 3 additional subjects who will be enrolled in the fasted group. All subjects in the food-effect cohort will receive active drug of TBAJ-876, 100 mg.

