### 3 ENDPOINTS

#### 3.1 Pharmacokinetic Endpoints

For Part 1 (single ascending dose including assessment of food effect), serial blood samples will be collected pre-dose and post-dose through 28 days to determine concentrations of TBAJ-876 and its metabolites (M2 and M3) in plasma. Additional samples were collected on Days 42, 56, and 70 for Cohorts 4, 5, and 6. For cohort 7, additional samples were only collected on Day 14. Noncompartmental pharmacokinetic parameters of  $AUC_{last}$ ,  $AUC_{inf}$ ,  $C_{max}$ ,  $T_{max}$ ,  $C_{last}$ ,  $T_{last}$ ,  $AUC_{Extrap\%}$ ,  $\lambda_z$ , and  $t_{1/2}$  will be calculated from plasma concentrations of TBAJ-876 (parent), M2 (metabolite), and M3 (metabolite);  $CL/F$  and  $V_z/F$  will be calculated for TBAJ-876 only.

For Part 2 (multiple ascending dose), serial blood samples will be collected pre-dose and post-dose through 24 hours on study days 1 and 14 to determine concentrations of TBAJ-876 and its metabolites (M2 and M3) in plasma. Predose trough plasma samples will be drawn daily Days 1 through 14.

For Part 2 on study day 1, noncompartmental pharmacokinetic parameters of  $AUC_{last}$ ,  $C_{max}$ ,  $T_{max}$ ,  $C_{last}$ ,  $T_{last}$ ,  $AUC_{tau}$ ,  $\lambda_z$ ,  $t_{1/2}$ , and  $C_{24}$  will be calculated from plasma concentrations of TBAJ-876 (parent), M2 (metabolite), and M3 (metabolite);  $CL/F$  and  $V_z/F$  may be calculated for TBAJ-876 if reasonable.

For Part 2 on study day 14, noncompartmental pharmacokinetic parameters of  $AUC_{tau}$ ,  $C_{max}$ ,  $T_{max}$ ,  $C_{min}$ ,  $C_{trough}$ ,  $C_{avg}$ ,  $C_{24}$ ,  $RAUC$ ,  $R_{C24}$ , and  $R_{Cmax}$  will be calculated from plasma concentrations of TBAJ-876 (parent), M2 (metabolite), and M3 (metabolite);  $CL_{ss}/F$  and  $V_z/F$  will be calculated for TBAJ-876 only. Parameters such as  $\lambda_z$ , and  $t_{1/2}$  may be calculated as reasonable.

For Part 3 (relative bioavailability [RBA] including assessment of food effect [FE]), serial blood samples will be collected pre-dose and post-dose through 14 days to determine concentrations of TBAJ-876 and its metabolites (M2 and M3) in plasma. Noncompartmental pharmacokinetic

QMD Ref: Worldwide-TMP-ST-006-4.0 Effective: 12Aug2019	Governing QMD: Worldwide-SOP-ST-001
Confidentiality Statement	

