## 6.2.11 Concentration-Time Data

Blood Samples for PK analysis in plasma will be collected at:

Part 1 (SAD):

- Predose, and 0.5, 1, 2, 3, 4, 5, 6, 8, 10, 12, 16, 20, 24, 28, 32, 36, 40, 44, 48, 54, 60, 66, 72, 80, 88, 96, 120, 144, and 168 hours after dosing, then on Days 10, 14, 17, 21 and 28.

Additional samples will be drawn on Days 42, 56, and 70 for Cohorts 4, 5, and 6.

- For Cohort 7, PK samples will be collected at predose (0), and 0.5, 1, 2, 3, 4, 5, 6, 8, 10, 12, 16, 20, 24, 28, 32, 36, 40, 44, 48, 54, 60, 66, 72, 80, 88, 96, 120, 144, and 168 hours (Day 14) after dosing.

Part 1 (FE):

- Predose, and 0.5, 1, 2, 3, 4, 5, 6, 8, 10, 12, 16, 20, 24, 28, 32, 36, 40, 44, 48, 54, 60, 66, 72, 80, 88, 96, 120, 144, and 168 hours after dosing, then on Days 10, 14, 17, 21 and 28.

Part 2 (MAD):

- Day 1: Predose, and 0.5, 1, 2, 3, 4, 5, 6, 8, 10, 12, 16, 20, 24 (pre-dose sample for Day 2).

QMD Ref: Worldwide-TMP-ST-006-4.0 Effective: 12Aug2019	Governing QMD: Worldwide-SOP-ST-001
Confidentiality Statement	

This document is the property of Worldwide Clinical Trials Inc. and may not be duplicated, copied, altered or removed from company without prior approval from Worldwide Quality Assurance or in compliance with Worldwide Standard Operating Procedures.

Worldwide Clinical Trials Controlled Quality Management Document		
 WORLDWIDE CLINICAL TRIALS	Sponsor:	Global Alliance for TB Drug Development
	Protocol Number:	TBAJ-876-CL001
STATISTICAL ANALYSIS PLAN – PHASE 1		

- Day 14: 0.5, 1, 2, 3, 4, 5, 8, 12, 16, 20, 24, 28, 32, 36, 40, 44, 48, 54, 60, 66, 72, 80, 88, 96, 120, 144, and 168 hours after dosing and on Days 42, 63, 84, 105, and 126.
- Additional or fewer samples may be collected at times to be determined based on the results from previous cohorts. Predose trough concentrations will be collected daily from Days 2 through 13.

Part 3 (RBA and FE):

- Pre-dose, and 0.5, 1, 2, 3, 4, 5, 6, 8, 10, 12, 16, 20, 24, 28, 32, 36, 40, 44, 48, 54, 60, 66, 72, 80, 88, 96, 120, 144, and 168 hours after dosing, then on Days 10 (240 h) and 14 (336 h).

Concentration-time data will be tabulated by part, nominal time, analyte, cohort (group for Part 3), and study day (for Part 2) using descriptive statistics. For presentation of the individual data and summary statistics, concentrations below the limit of quantitation (BLQ) will be set to zero.

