### 6.2.12.2 Part 2 PK Parameters

#### 6.2.12.2.1 Study Day 1 PK Parameters (Part 2)

The following PK parameters will be calculated for TBAJ-876, M2, and M3 for Part 2 (Day 1):

Parameter	Definition
C max	Maximum plasma concentration, determined directly from individual concentration-time data
T max	Time of the maximum plasma concentrations

QMD Ref: Worldwide-TMP-ST-006-4.0 Effective: 12Aug2019	Governing QMD: Worldwide-SOP-ST-001
Confidentiality Statement	

This document is the property of Worldwide Clinical Trials Inc. and may not be duplicated, copied, altered or removed from company without prior approval from Worldwide Quality Assurance or in compliance with Worldwide Standard Operating Procedures.

Worldwide Clinical Trials Controlled Quality Management Document			
 WORLDWIDE CLINICAL TRIALS	Sponsor:	Global Alliance for TB Drug Development	
	Protocol Number:	TBAJ-876-CL001	
STATISTICAL ANALYSIS PLAN – PHASE 1			

Parameter	Definition
$C_{last}$	Last quantifiable plasma concentration determined directly from individual concentration-time data
$T_{last}$	Time of last quantifiable plasma concentration
$AUC_{0-24h}$ ( $AUC_{tau}$ )	Area under the plasma concentration-time curve over the 24 hour dosing interval, calculated using the linear trapezoidal rule
$C_{avg}$	Average plasma concentration over 24 hours
$C_{24}$	Plasma concentration at 24 hours postdose
$\lambda_z$ ( $K_{el}$ , Lambda z)	
The apparent elimination rate constant <math>\lambda_z</math> will be calculated as the negative of the slope of the linear regression through the terminal log-linear segment of the plasma concentration-time curve; the range of data to be used will be determined by visual inspection of a semi-logarithmic plot of concentration vs. time
 
(see additional criteria in Section 6.2.12.3)
 
(may be calculated as reasonable)

$t_{1/2}$	
The observed terminal elimination half-life, calculated as:
 $t_{1/2} = \ln(2)/\lambda_z$ 
(may be calculated as reasonable)

$CL/F$	
The apparent total plasma clearance after an oral dose, calculated as:
 $CL/F = Dose/AUC_{inf}$ , where F is the bioavailability 
(calculated for parent only, may be calculated as reasonable)

$Vz/F$	
The apparent volume of distribution after an oral dose, calculated as:
 $Vz/F = Dose/(AUC_{inf} \times \lambda_z)$ , where F is the bioavailability 
(calculated for parent only, may be calculated as reasonable)

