#### **6.2.12.4 Lambda-z ( $\lambda_z$ ) Acceptance and AUCinf Reporting Criteria**

The following criteria will be used to report lambda-z and related parameters:

- At least 3 quantifiable concentration-time points should be used in the regression
- Cmax or data prior to Cmax should not be included in the regression
- Adjusted R^2 should be  $\geq 0.8000$

If these acceptance criteria are not met, lambda-z and descriptive parameters such as the time range for the regression, adjusted R^2, etc. will be retained in a parameter listing for informational purposes. Lambda-z will be excluded from summary statistics and from subsequent PK calculations; parameters calculated using lambda-z (e.g. t1/2, AUCinf, CL/F, and Vz/F) will be reported as ND (not determinable).

If lambda-z acceptance criteria are met and AUCinf is estimable, the following criteria are used to report AUCinf:

- The percentage of AUCinf based on extrapolation should be  $<20.0\%$ .

If the percentage of AUCinf based on extrapolation is 20.0% or greater, AUCinf and AUCExtrap will be retained in a PK parameter listing for informational purposes; these parameters will be excluded from summary statistics, subsequent PK calculations (e.g., CL/F, Vz/F), and statistical analysis (e.g. ANOVA).

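### Part 2 Day 1 lambda-z and half-life rest on 24 hours of sampling, and the SAP acceptance rules cannot tell a distribution slope from a terminal one

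*SAP*

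**What the plan says.** - **Sampling.** SAP 6.2.11 gives the Part 2 times as "Day 1: Predose, and 0.5, 1, 2, 3, 4, 5, 6, 8, 10, 12, 16, 20, 24 (pre-dose sample for Day 2". The profile cannot run longer, because the second dose follows.
- **Half-life.** Protocol section 3, under Part 1, "assumes that the terminal half-life ($T_{1/2}$) will be approximately 7 days". That sentence concerns Part 1 scheduling, but the drug is the same.
- **Animal data.** Protocol 1.5 describes disposition as multiexponential and says that half-life estimates "varied widely, ranging from 5 to 12 hr (sampling out to 24 hr postdose) to 26 to 77 hr (sampling out to 96 hr postdose".
- **Day 1 parameters.** SAP 3.1 lists lambda-z and half-life without condition for all three analytes. Only CL/F and Vz/F "may be calculated for TBAJ-876 if reasonable". The table in SAP 6.2.12.2.1 makes lambda-z and half-life optional too, and marks CL/F and Vz/F "calculated for parent only, may be calculated as reasonable". Protocol 9.2 and the synopsis also make these parameters optional (naming CLss/F where the SAP has CL/F). No passage defines the condition.
- **Choice of regression points.** In the Day 1 table, "the range of data to be used will be determined by visual inspection of a semi-logarithmic plot of concentration vs. time".
- **Acceptance.** SAP 6.2.12.4 has three lambda-z rules: "At least 3 quantifiable concentration-time points should be used in the regression"; Cmax and earlier points are left out; adjusted R-squared is at least 0.80. A separate rule drops AUCinf, and with it CL/F and Vz/F, when the extrapolated share is 20% or more.
- **Cross-reference.** The Day 1 table points to 6.2.12.3 for the criteria. That section is the Part 3 parameter table. The Part 1 and Day 14 tables make the same slip.
- **Outputs.** Listing 16.2.6.5 gives Day 1 terminal rates, and Tables 14.4.8.1 and 14.4.8.2 give Day 1 parameters. Regression plots (Figures 14.4.23 to 14.4.25) are planned for Part 1, Part 2 Day 14 and Part 3, but not for Part 2 Day 1.

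**The concern.** The protocol's own animal data show what 24 h sampling does to this compound: the half-life comes out several times shorter than with 96 h sampling, because the fitted slope belongs to distribution. The Part 2 Day 1 window has the same length. A declining log-linear segment between Cmax and 24 h can satisfy all three lambda-z rules without being terminal.

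The 20% rule looks like a backstop but is only a partial one. It acts on AUCinf and what is computed from it, so lambda-z and half-life never meet it. For CL/F and Vz/F it uses the same doubtful slope: the steeper the early slope, the smaller the extrapolated share appears, and the easier the rule is to pass.

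At stake is a listed and summarised Part 2 half-life, and sometimes a clearance, that describes early distribution and carries the label of a terminal parameter.

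**Working it through.** The documents give no figure for this point and the study is not formally powered, so there is nothing to reproduce. The checks are these.

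**1. Window against half-life.** With a half-life of 7 days = 168 h, lambda-z = ln2/168 = 0.00413 per h, and 24/168 = 0.14 half-lives. A mono-exponential curve falls by 1 − 2^(−24/168) = 9.4% over 24 h, and by 1 − 2^(−12/168) = 4.8% between 12 and 24 h.

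**2. When the 20% rule acts (bolus, mono-exponential).** Extrapolated share = 2^(−24/t½). At the true 168 h this is 90.6%, so CL/F and Vz/F are removed. The share falls below 20% only if the apparent half-life is under 24 × ln2/ln5 = 10.3 h. The rule therefore removes CL/F when the slope is right and passes it when the slope is much too steep.

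**3. The protocol's own predictions (section 1.4, notes to Table 1).**
- Day 1 AUC0-24h at 400 mg is 10.4 µg·h/mL. Scaled linearly to 25 mg: 10.4 × 25/400 = 0.65.
- Day 28 AUC0-24h at 25 mg daily is 2.1. With linear, time-constant kinetics this does not exceed the single-dose AUCinf, so at most 0.65/2.1 = 31% of AUCinf is seen by 24 h.
- An AUCinf that passes the 20% rule is at most 0.65/0.80 = 0.81, so CL/F is overstated at least 2.1/0.81 = 2.6-fold.

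**4. Bi-exponential oral profiles on the Day 1 sampling times.** The parameters are assumed: terminal half-life 168 h; absorption rate 0.3 or 0.6 per h; fast-phase half-life 2, 3, 4, 5, 8 or 12 h; fast-phase fraction 0.80, 0.90, 0.95 or 0.98. That makes 2 × 6 × 4 = 48 noiseless profiles. AUC is by linear trapezoid. The regression used the post-Cmax window of at least 3 points with the best adjusted R-squared, standing in for the SAP's visual choice.

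- Lambda-z and half-life accepted: 48 of 48. Adjusted R-squared 0.88 to 1.00; apparent half-life 4.1 to 81 h.
- CL/F passes the 20% rule: 24 of 48 (one at 19.9%), with apparent half-lives of 4.1 to 9.5 h. All 24 are overstated, 1.3- to 4.0-fold. The other 24 are removed.
- Example (absorption 0.3 per h, fast phase 4 h, fraction 0.90): apparent half-life 8.7 h, adjusted R-squared 0.994, apparent extrapolation 18.2%, true extrapolation 76.2%. Overstatement of CL/F = (1 − 0.182)/(1 − 0.762) = 3.4.
- Of the 24 profiles that pass, 19 have a regression spanning at least two apparent half-lives.

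**5. With noise (log-normal, 5 to 15%, 4,000 runs per setting).** For selected bi-exponential profiles, lambda-z is accepted in 84 to 100% of runs, and CL/F is reported in 0 to 100% depending on the fast phase. For a purely mono-exponential 168 h profile, lambda-z is accepted in only 10 to 16% of runs (median accepted half-life 25 to 69 h) and CL/F is never reported.

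**6. Day 14 CLss/F as the substitute.** Fourteen days is two assumed half-lives. If mono-exponential, AUCtau on Day 14 is 1 − 2^(−14/7) = 75% of its steady-state value, so Dose/AUCtau overstates clearance by up to 1/0.75 = 1.33-fold. Protocol 1.7 also predicts AUCs rising through Day 14.

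**The case against.** The strongest reply is that the calculation is discretionary. The Day 1 table, protocol 9.2 and the synopsis make all four parameters optional, and the analyst chooses the terminal segment by eye, with Part 1 profiles to Day 28 or Day 70 for comparison. A careful analyst may report nothing. This stands as far as it goes, but SAP 3.1 still makes lambda-z and half-life unconditional, the condition is undefined, and a listing is already planned.

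A second reply concerns the simulation. Its parameters are assumed, and an automatic window is not the SAP's visual method. Profiles close to the protocol's predicted shape sit near the 20% limit: extrapolated shares of 24.2% (removed) and 19.9% (passes). The fold-errors therefore show what the rules can let through; they do not estimate this trial's error.

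Two stronger readings are tempting. A reader might infer that the rules screen out none of the four parameters. They do remove CL/F and Vz/F in half of the assumed profiles, and the R-squared rule rejects most mono-exponential fits. A reader might also infer that a Day 1 half-life set beside the Day 14 one would produce a false finding of change over time. No such comparison is planned, and Day 14 half-life is itself optional. Part 2 dose proportionality uses Cmax and AUCtau, the accumulation ratios use AUCtau, Cmax and C24, and steady state uses troughs. None needs Day 1 lambda-z.

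**Conclusion.** The point holds for lambda-z and half-life. As written, the plan can accept and report a distribution-phase slope as a terminal half-life, and none of its criteria detects this. In the assumed profiles the reported value was 4 to 81 h against a true 168 h. This rests on a half-life near 7 days and on multi-phase disposition in humans, which the protocol reports only for animals.

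For CL/F and Vz/F the protection is unreliable rather than absent. The 20% rule removed them in about half of the profiles, and each CL/F that passed was too high: 1.3- to 4.0-fold under the assumed parameters, or at least 2.6-fold if the protocol's predictions are scaled linearly with dose.

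The damage is confined to the Day 1 parameter tables and listing. The change should be made, but no main Part 2 conclusion depends on it.

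**What to change.** - Delete lambda-z, half-life, CL/F and Vz/F from the Part 2 Day 1 lists in SAP 3.1 and 6.2.12.2.1, and delete Listing 16.2.6.5. This also removes the conflict between the two sections, the undefined condition, and the use of AUCinf, which is not a listed Day 1 parameter.
- Report Part 2 half-life from the Day 14 washout, sampled to Day 126.
- Take single-dose CL/F from Part 1 where the AUCinf criteria are met. Part 2 is dosed fed, so the fed group of the food-effect cohort is the like-for-like source.
- Label Day 14 CLss/F as possibly not at steady state, with the 1.33-fold bound.
- Correct the cross-references from 6.2.12.3 to 6.2.12.4 in the Day 1 and Day 14 tables, and likewise in the Part 1 table.

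A minimum-span rule alone would not do: 19 of the 24 wrongly passing profiles already span two apparent half-lives, because a short apparent half-life makes the span look long.

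The cost is SAP wording and one fewer listing. The protocol wording is permissive and needs no amendment; a line in SAP section 7 can record that the optional Day 1 parameters will not be derived.

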### 6.2.12.2.2 Study Day 14 PK Parameters (Part 2)

The following PK parameters will be calculated for TBAJ-876, M2, and M3 for Part 2 (Day 14):

Parameter	Definition
$C_{\max}$	Maximum plasma concentration, determined directly from individual concentration-time data
$T_{\max}$	Time of the maximum plasma concentrations
$C_{\min}$	Minimum plasma concentration, determined directly from individual concentration-time data
$AUC_{\text{tau}}$	Area under the plasma concentration-time curve over the 24 hour dosing interval, calculated using the linear trapezoidal rule
$C_{\text{avg}}$	Average plasma concentration over 24 hours
$C_{24}$	Plasma concentration at 24 hours postdose
$C_{\text{trough}}$	Predose plasma concentration, (Days 2-14)
$\lambda_z$ ( $K_{\text{el}}$ , Lambda z)	The apparent elimination rate constant $\lambda_z$ will be calculated as the negative of the slope of the linear regression through the terminal log-linear segment of the plasma concentration-time curve; the range of data to be used will be determined by visual inspection of a semi-logarithmic plot of concentration vs. time  (see additional criteria in Section 6.2.12.3)  (may be calculated as reasonable)
$t_{1/2}$	The observed terminal elimination half-life, calculated as: $t_{1/2} = \ln(2)/\lambda_z$ (may be calculated as reasonable)
$CL_{\text{ss}}/F$	The apparent total plasma clearance after an oral dose at steady-state, calculated as:

QMD Ref: Worldwide-TMP-ST-006-4.0 Effective: 12Aug2019	Governing QMD: Worldwide-SOP-ST-001
Confidentiality Statement	

This document is the property of Worldwide Clinical Trials Inc. and may not be duplicated, copied, altered or removed from company without prior approval from Worldwide Quality Assurance or in compliance with Worldwide Standard Operating Procedures.

Worldwide Clinical Trials Controlled Quality Management Document					
 WORLDWIDE CLINICAL TRIALS	Sponsor:	Global Alliance for TB Drug Development			
Protocol Number: TBAJ-876-CL001					
STATISTICAL ANALYSIS PLAN – PHASE 1					

Parameter	Definition
	CLss/F=Dose/AUC tau , where F is the bioavailability (calculated for parent only)
Vz/F	The apparent volume of distribution after an oral dose at steady-state, calculated as: Vz/F=Dose/(AUC inf x λ z ), where F is the bioavailability (calculated for parent only)
R AUC	Accumulation ratio of AUC tau for Day 14, calculated as: AUC tau (Day 14)/AUC tau (Day 1)
R C24	Accumulation ratio of R C24 for Day 14, calculated as: C 24 (Day 14)/ C 24 (Day 1)
R Cmax	Accumulation ratio of C max for Day 14, calculated as: C max (Day 14)/ C max (Day 1)

